### 8.3.9. Clinical Safety Laboratory Assessments

All protocol required laboratory assessments, as defined in [Table 11](#), must be conducted in accordance with the Laboratory Manual, and Protocol Time and Events Schedule. Laboratory requisition forms must be completed and samples must be clearly labelled with the subject number, protocol number, site/centre number, and visit date. Details for the preparation and shipment of samples will be provided by the laboratory and are detailed in the Laboratory Manual. Reference ranges for all safety parameters will be provided to the site by the laboratory responsible for the assessments.

If additional non-protocol specified laboratory assessments are performed at the institution's local laboratory and result in a change in subject management or are considered clinically significant by the investigator (e.g., SAE or AE or dose modification) the results must be recorded in the CRF.

Refer to the Laboratory Manual for appropriate processing and handling of samples to avoid duplicate and/or additional blood draws.

All protocol required safety laboratory assessments, as defined in [Table 11](#), are performed at the institution's local laboratory. All non-safety assessments (e.g., pharmacokinetic samples and translational samples) will be assessed by a central laboratory. Please refer to the Laboratory Manual for appropriate processing and handling of samples to avoid duplicate and/or additional blood draws.

Some laboratory assessments (e.g., testosterone) can vary throughout the day. It is recommended but not mandated that laboratory assessments are collected at approximately the same time on each clinic day. If abnormal testosterone levels are observed, repeat measurements should occur at the approximate baseline timing to ensure this is a trend and not a single outlying event.

**Table 11 Clinical Laboratory Tests**

Serum Chemistry			
Blood urea nitrogen	Magnesium	aspartate aminotransferase	Total and direct bilirubin
Sodium	Potassium		Uric acid
Creatinine	Chloride	alanine aminotransferase	Albumin
Fasting Glucose	Total carbon dioxide	alkaline phosphatase	Total protein
Creatine phosphokinase	Ionized calcium	gamma-glutamyltransferase	Total calcium
Hematology			
Platelet count	Automated White Blood Cell		
Red blood cell count	Differential:		
White blood cell count (absolute)	Neutrophils (absolute)		
Hemoglobin	Lymphocytes (absolute)		
	Monocytes (absolute)		
	Eosinophils (absolute)		
	Basophils (absolute)		
Routine Urinalysis			
Specific gravity			
pH, glucose, protein, blood, and ketones by dipstick			
Microscopic examination (if blood or protein is abnormal)			
Other Tests			
Coagulation tests (prothrombin time, partial thromboplastin time, international normalized ratio, and fibrinogen)			
Pancreatic markers (amylase and lipase)			
Fasting_Lipid panel (triglycerides and total cholesterol, low density lipoprotein [LDL], high density lipoprotein [HDL])			
C-Peptide			
Troponin (I or T at local laboratory, Troponin T at central laboratory)			
Insulin			
Hemoglobin A1C			
1,5 -Anhydroglucitol (1,5 AG)			
NT-proBNP			
Thyroid-stimulating hormone (TSH)			
Free Thyroxine 3 (Free T3)			
Free Thyroxine 4 (Free T4)			
Creatine kinase (CK)			
Creatine Kinase-MB isoenzyme (CK-MB)			
Testosterone for males (free and complete testosterone at prior to first dose, free testosterone after first dose)			
Pregnancy test for females (serum at screening, Urine or serum post dose)			
Cytokine samples			

Subjects should be instructed to fast (no food and only water allowed) for 10 hours prior to any fasting laboratory assessments (e.g., fasting glucose, fasting lipid panel, etc.).

All laboratory results that are considered by the investigator clinically significantly abnormal during participation in the study or within 28 days after the last dose of study treatment should be recorded on the eCRF as AEs. In addition, these clinically significant abnormal laboratory results should be followed until the abnormality resolves or is determined to be stable. If such values do not return to normal within a period judged reasonable by the investigator, the etiology should be identified and the sponsor notified.

### 8.3.10. Troponin Measurement

. At W1D1 and W1D2 three local lab troponin samples (8hrs apart) should be drawn per day but only 1 central lab sample should be drawn per day. At other time-points (including unscheduled visit) only two samples should be drawn; 1 for local lab analysis and 1 for central lab analysis. Troponin T will be assessed at a central laboratory as a means of consistent evaluation across all subjects Whereas second sample, assessed at a local laboratory, will be used for purpose of subject management. Whenever possible, troponin T will be assayed by the local laboratory. However, either troponin I or troponin T may be assessed at a local laboratory. The same local laboratory test (troponin I or troponin T) should be used consistently for an individual subject throughout the study.

### 8.3.11. Pregnancy

- Reporting of any pregnancies in female subjects and/or female partners of male subjects will be collected after the start of dosing and until 7 months following the last dose of GSK2820151.
- If a pregnancy is reported then the investigator should inform GSK within 2 weeks of learning of the pregnancy. The subject will also be followed to determine the outcome of the pregnancy. Information on the status of the mother and child will be forwarded to GSK. Generally, follow-up will be no longer than 6 to 8 weeks following the estimated delivery date. Any premature termination of the pregnancy will be reported. Details on follow-up procedures outlined in [Appendix 7](#).

## 8.4. Pharmacokinetics

PK analyses will be the responsibility of GSK Clinical Pharmacokinetics Modeling & Simulation (CPMS). Plasma GSK2820151 concentration-time data will be analyzed by non-compartmental methods with WinNonlin.

From the plasma concentration-time data, the following pharmacology parameters will be determined, as data permit: maximum observed plasma concentration ( $C_{max}$ ), time to  $C_{max}$  ( $t_{max}$ ), area under the plasma concentration-time curve ( $AUC_{(0-\tau)}$  and  $AUC_{(0-\infty)}$  Week 1 Day 1 only) and apparent terminal phase half-life ( $t_{1/2}$ ). Trough concentration ( $C_{\tau}$ ) samples collected on the specified days will be used to assess attainment of steady state. To estimate the extent of accumulation after repeat dosing, the observed accumulation ratio ( $R_o$ ) may be determined from the ratio of  $AUC_{(0-\tau)}$  in Week 3 Day 4 /  $AUC_{(0-\tau)}$  in Week 1 Day 1. The ratio of  $AUC_{(0-\tau)}$  on Week 3 Day 4/ Week 1 Day 1  $AUC_{(0-\infty)}$  will be calculated to assess time invariance. GSK2820151 concentrations will be determined in urine samples to determine urinary recovery of unchanged drug and renal clearance.

Plasma concentration-time data will be listed by dose and summarized using descriptive statistics (n, mean, standard deviation [SD], median, minimum and maximum) by planned relative assessment time. Mean and/ or median values will be plotted over time. Individual plasma and urinary (if available) PK parameters values as well as a descriptive summary (mean, standard deviation, median, minimum, maximum, geometric mean, and the standard deviation, CV% and 95% confidence interval of log-transformed parameters [if applicable]) by dose cohort will be reported.

Cmax and AUC (AUC(0-∞), single dose, and AUC(0-τ), steady state) will be plotted as a function of the dose administered. If more than 2 dose cohorts are evaluated, dose proportionality of AUC and Cmax for GSK2820151 will be assessed using the power model (details will be provided in the Reporting and Analysis Plan [RAP]).

Plasma concentration-time data will be further analyzed using appropriate model(s) to determine population PK parameters (absorption rate (Ka), apparent clearance (CL/F) and volume of distribution (V/F)) and summary exposure measures (Cmax, AUC and Average observed concentration [Cav] = AUC/τ) and identify important covariates (e.g., age, weight, or disease related covariates).

#### **8.4.1. Blood Sample Collection for Pharmacokinetics**

Blood samples for PK analysis of GSK2820151 will be collected at the time points indicated in the Time and Events Schedule ([Table 9](#) and [Table 10](#)).

Each PK sample should be collected as close as possible to the planned time relative to the dose (i.e., time zero) administered to the subject on PK days. The actual date and time of each blood sample collection will be recorded along with the date and time of the prior dose administration. The timing of PK samples may be altered and/or PK samples may be obtained at additional time points to ensure thorough PK monitoring. This will not require a protocol amendment. In addition, plasma samples may be analyzed qualitatively for other circulating compound-related material and the results will be reported under a separate Drug Metabolism and Pharmacokinetics (DMPK) protocol.

Details on PK blood sample collection, processing, storage, and shipping procedures are provided in the Laboratory Manual.

#### **8.4.2. Urine Sample Collection for Pharmacokinetics**

Urine samples for quantitative analysis of GSK2820151 will be collected over 24 hours in two samples (sample collected 0-2 hr and a second sample collected 2-24 hr) immediately following dosing on Week 1 Day 1 and Week 3 Day 4

The actual date and time of each urine sample collection will be recorded. In addition, pooled urine pH, the total volume of the pooled urine and the weight of the pooled urine will be measured and recorded in the eCRF.

Details of urine sample collection, processing, storage, and shipping procedures are provided in the Laboratory Manual.

#### **8.4.3. Pharmacokinetic Sample Analysis**

Plasma sample analysis will be performed under the management of Bioanalytical Science and Toxicokinetics, Drug Metabolism and Pharmacokinetics (DMPK), Platform Technology and Science (PTS), GlaxoSmithKline. Concentrations of GSK2820151 will be determined in plasma samples using the currently approved bioanalytical

methodology. Raw data will be stored in the Good Laboratory Practices (GLP) Archives, GlaxoSmithKline.

Once the plasma samples have been analyzed for GSK2820151, any remaining plasma may be analyzed for other compound-related metabolites and the results reported under a separate GSK PTS-DMPK protocol.

Urine sample analysis may be performed under the management of Bioanalytical Science and Toxicokinetics, DMPK, PTS, GlaxoSmithKline. Concentrations of GSK2820151 may be determined in urine samples using an investigative analytical methodology. Urine raw data will be stored in the GLP Archives, GlaxoSmithKline.

The urine samples may be analyzed for compound-related metabolites and the results will be reported under a separate DMPK protocol.

## **8.5. Pharmacokinetic/Pharmacodynamic Analysis**

Observed or predicted concentrations and/or exposures will be combined with safety, efficacy, and/or PD measures of interest to examine potential exposure response relationships.

The relationship between QTcF and concentration expressed as  $C_{max}$ ,  $C_{av}$ , and instantaneous time-matched concentration will be plotted graphically. A linear mixed effects analysis of the slope of the QTcF-concentration responses adjusting for baseline will be evaluated as a means of estimating QTcF effect in lieu of a thorough QT study.

Other quantitative safety parameters and biomarkers of interest including changes in troponin levels will be plotted graphically against summary exposure measures (e.g.,  $C_{max}$ ,  $C_{\tau}$ , and  $C_{av}$ ). Where evidence of a signal is seen, linear and non-linear mixed effect models will be fitted to the data to estimate PK/PD parameters of interest; slope, baseline ( $E_0$ ), exposure producing 50% of the maximum effect ( $EC_{50}$ ), and maximum effect ( $E_{max}$ ).

Overall efficacy data and overall tumor burden may be described using ordered categorical model and continuous models with summary exposure parameters (e.g.,  $C_{max}$ ,  $C_{\tau}$ , and  $C_{av}$ ) as covariates derived from the population PK analysis. Further model details will be provided in the RAP.

## **8.6. Efficacy**

The overall response rate is defined as the percentage of subjects with a confirmed complete response (CR) or a partial response (PR) at any time as per RECIST 1.1.

- Lesion assessment will be conducted according to Response Evaluation Criteria in Solid Tumors (RECIST 1.1) [[Eisenhauer, 2009](#)] as outlined below and in [Appendix 8](#).

- Disease assessment modalities may include imaging (e.g., computed tomography [CT] scan, magnetic resonance imaging [MRI], bone scan, plain radiography) and physical examination (as indicated for palpable/superficial lesions).
- The baseline disease assessment will be completed within 2 weeks prior to the first dose of GSK2820151, then every 8 weeks starting W1D1 thereafter, and at the final study visit. See the Time and Events Table (Section 8.1) for the schedule of assessments of anti-cancer activity.
- For subjects with CRPC without measurable disease by RECIST criteria, serial prostate specific antigen (PSA) measurements will be drawn at the disease assessment time points defined in the Time and Events Table (Section 8.1). Response will be defined by the number of subjects who achieve a 50% decrement in their baseline PSA (PSA50).
- Assessments must be performed on a calendar schedule and should not be affected by dose interruptions/delays.
- For post-baseline assessments, a window of  $\pm 7$  days is permitted to allow for flexible scheduling. If the last radiographic assessment was more than 8 weeks prior to the subject's withdrawal from study and progressive disease has not been documented, a disease assessment should be obtained at the time of withdrawal from study.
- Subjects whose disease responds (either complete response [CR] or partial response [PR]) should have a confirmatory disease assessment performed 4 weeks after the date of assessment during which the response was demonstrated. More frequent disease assessments may be performed at the discretion of the investigator.
- To ensure comparability between the baseline and subsequent assessments, the same method of assessment and the same technique will be used when assessing response.

## 8.7. Translational Research

The results of translational research investigations may be reported separately from the main clinical study report or as an amendment. All endpoints of interest from all comparisons will be descriptively and/or graphically summarized as appropriate to the data. Further details on the translational research analyses will be addressed in the RAP.

### 8.7.1. Biologic Effects of GSK2820151

Exploratory analysis may be performed to examine potential relationships between drug exposure and markers of BET target inhibition (e.g., cytokines, acute phase proteins, relevant transcripts, and/or proteins) or between anticancer activity and potential markers of sensitivity (e.g., genetic alterations).

### 8.7.2. RNA Expression Research

Related BET inhibitors have been shown to modulate the expression of a number of different genes in unstimulated whole blood between 1 h and 6 h. The mRNA levels of 31 such genes form a 'signature' panel which will also be used as a biomarker of engagement of pharmacology and will be measured using mRNA isolated from whole

blood. The modulation of a number of these genes will also be measured as changes in systemic proteins as well as in the analysis of the ex vivo assay blood samples (e.g., Chemokine [C-C motif] ligand 2 [CCL2] and Interleukin 8 [IL-8]) thus relating mRNA and protein expression with drug concentration. Other translational research studies, such as transcriptomics profiling, will also be performed using whole blood mRNA from selected patients.

### **8.7.3. Effects of GSK2820151 on Systemic Markers of Inflammation**

GSK2820151 has been shown to inhibit LPS-induced IL-6 across different human cell populations and species. The action of the compound is through inhibition of the assembly of transcriptional complexes required to express the protein. Pre-clinical studies demonstrate that blood concentration of drug correlates to the degree of inhibition of LPS induced IL-6 in ex vivo whole blood samples. Therefore, this biomarker will be used as an indication of pharmacology and will be aligned with PK sampling. Since inhibition of BET family proteins is known to inhibit a range of pro-inflammatory mediators and acute phase proteins, a number of additional proteins (46) will also be measured from these ex vivo samples.

The set of analytes identical to that used in the whole blood ex vivo assay (including for example, CCL2, macrophage inflammatory protein 1 alpha [MIP1- $\alpha$ ], IL-8) will also be measured in plasma samples taken during PK sampling and at the time of any Grade 2 fever or symptoms indicative of a potential cytokine storm. This will assess systemic inflammatory response in the subject using biomarkers such as pro-inflammatory cytokines and acute phase proteins and correlate the systemic response to drug with that in stimulated and unstimulated blood. These biomarkers are expected to change over days rather than hours, based on the plasma half lives and pre-clinical data, such that sampling will also be performed after repeat dosing.

## **8.8. Pharmacogenetic Analysis**

An important objective of the clinical study is pharmacogenetic (PGx) research. Participation in PGx is optional but all subjects who are eligible for the clinical study will be given the opportunity to participate. Subjects may decline participation without effect on their medical care or care during the clinical study. A separate consent signature is required for PGx research.

Subjects who provide consent will have a blood sample taken for analysis. The presence/absence of genetic variations in host deoxyribonucleic acid (DNA) from blood will be analyzed to determine their relationship with response (safety, tolerability, pharmacokinetics, and efficacy) to treatment with GSK2820151.

Information regarding pharmacogenetic research is included in [Appendix 5](#). In approving the clinical protocol, the independent ethics committee/institutional review board (IEC/IRB) (and, where required, the applicable regulatory agency) also approve the PGx assessments unless otherwise indicated. Where permitted by regulatory authorities, approval of the PGx assessments can occur after approval is obtained for the rest of the study. If so, then the written approval will clearly indicate approval of the PGx assessments is being deferred and the study, except for PGx assessments, can be initiated.

When PGx assessments are not approved, then the approval for the rest of the study will clearly indicate this and therefore, PGx assessments will not be conducted.

Information regarding genetic research is included in [Appendix 5](#)

## **9. ADVERSE EVENTS AND SERIOUS ADVERSE EVENTS: DATA COLLECTION, REPORTING, AND FOLLOW-UP**

### **9.1. Definition of AE/SAE**

The definitions of an AE or SAE can be found in [Appendix 6](#). The severity of adverse events will be graded utilizing the NCI-CTCAE v4.03. Additional details regarding management of specific AEs or SAEs are described in [Appendix 7](#).

The investigator and their designees are responsible for detecting, documenting and reporting events that meet the definition of an AE or SAE.

#### **9.1.1. Cardiovascular and Death Events**

For any cardiovascular events detailed in [Appendix 6](#) and all deaths, whether or not they are considered SAEs, specific Cardiovascular (CV) and Death sections of the eCRF will be required to be completed. These sections include questions regarding cardiovascular (including sudden cardiac death) and non-cardiovascular death.

The CV eCRFs are presented as queries in response to reporting of certain CV Medical Dictionary for Regulatory Activities (MedDRA) terms. The CV information should be recorded in the specific cardiovascular section of the CRF within one week of receipt of a CV Event data query prompting its completion.

The Death eCRF is provided immediately after the occurrence or outcome of death is reported. Initial and follow-up reports regarding death must be completed within one week of when the death is reported.

#### **9.1.2. Other Sentinel Events**

Any abnormal laboratory test results (hematology, clinical chemistry, or urinalysis), or other safety assessments (e.g., ECGs, radiological scans, vital signs measurements) including those that worsen from baseline, and events felt to be clinically significant in the medical and scientific judgment of the investigator are to be recorded as an AE or SAE, in accordance with the definitions provided.

In addition, an associated AE or SAE is to be recorded for any laboratory test result or other safety assessment that led to an intervention, including permanent discontinuation of study treatment, dose reduction, and/or dose interruption/delay.

Any new primary cancer must be reported as a SAE.

### 9.1.3. Disease-Related Events and/or Disease-Related Outcomes Not Qualifying as SAEs

Any clinically significant safety assessments that are associated with the underlying disease, unless judged by the investigator to be more severe than expected for the subject's condition, are not to be reported as AEs or SAEs.

*NOTE: If either of the following conditions apply, then the event must be recorded and reported as an SAE (instead of a DRE):*

- *The event is, in the investigator's opinion, of greater intensity, frequency, or duration than expected for the individual subject, or*
- *The investigator considers that there is a reasonable possibility that the event was related to treatment with the investigational product*

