**Serious Adverse Event (SAE) is defined as any untoward medical occurrence that, at any dose:**

**a. Results in death****b. Is life-threatening**

NOTE:

The term 'life-threatening' in the definition of 'serious' refers to an event in which the subject was at risk of death at the time of the event. It does not refer to an event, which hypothetically might have caused death, if it were more severe.

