### 14.6.5. Evaluating AEs and SAEs

#### Assessment of Intensity

The investigator will make an assessment of intensity for each AE and SAE reported during the study and will assign it to one of the following categories:

- Mild: An event that is easily tolerated by the subject, causing minimal discomfort and not interfering with everyday activities.
- Moderate: An event that is sufficiently discomforting to interfere with normal everyday activities
- Severe: An event that prevents normal everyday activities. - an AE that is assessed as severe will not be confused with an SAE. Severity is a category utilized for rating the intensity of an event; and both AEs and SAEs can be assessed as severe.
- An event is defined as 'serious' when it meets at least one of the pre-defined outcomes as described in the definition of an SAE.

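### The Section 9.1.3 NOTE makes disease-related events SAEs with no seriousness test and contradicts Appendix 6 in two ways, so such events could be misclassified or left unreported.

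*Protocol*

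**What the plan says.** Protocol Section 9.1.3 opens with a broad class, "Any clinically significant safety assessments that are associated with the underlying disease", and says these are not reported as AEs or SAEs unless the investigator judges them more severe than expected. A NOTE follows with two alternative triggers. One is that the event is "of greater intensity, frequency, or duration than expected for the individual subject". The other is that "there is a reasonable possibility that the event was related to treatment with the investigational product". If either applies, "then the event must be recorded and reported as an SAE (instead of a DRE"). The NOTE names no seriousness outcome and no AE alternative. DRE is not defined there or in the Appendix 1 abbreviations.

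Section 9.1 says "The definitions of an AE or SAE can be found in" Appendix 6. In that appendix:

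- 14.6.1 lists disease-associated findings, and the expected course of the disease under study, among events that are not AEs. The only exception is greater severity than expected.
- 14.6.2 begins "Serious Adverse Event (SAE) is defined as any untoward medical occurrence that, at any dose" and lists the qualifying outcomes. It also states that something that is not an AE cannot be an SAE, even when a serious outcome is present. Its examples are hospitalization for disease symptoms and death from progression.
- 14.6.5 says an event is serious "when it meets at least one of the pre-defined outcomes as described in the definition of an SAE".

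**The concern.** SAE status normally depends on outcome. Causality and expectedness are separate judgements. The NOTE lets either of those judgements alone make an event an SAE, which Appendix 6 does not allow. Two sites could each follow the protocol and classify the same event differently.

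SAEs are a named component of the primary endpoint (Section 3). They are reported to the sponsor within 24 hours (Section 9.2), evaluated for causality by the Safety Review Team (Section 5.4.5), summarized separately under Protocol 11.5.2.5, and listed under SAP Section 11.4 (Listings 24 and 25). The error can run both ways. Non-serious events may be filed as SAEs, or a serious event that may be drug-related may be withheld as disease-related.

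**Working it through.** No figure in the plan bears on this, so the check sets the rules side by side. For a disease-associated event, the outcome depends on three judgements: worse than expected or not, possibly related or not, and whether a listed seriousness outcome is met.

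| Event | 9.1.3 lead sentence | 9.1.3 NOTE | Appendix 6 |
|---|---|---|---|
| Worse than expected, serious | Exemption lifted | SAE | SAE |
| Worse than expected, not serious | Exemption lifted | SAE | AE only |
| Expected severity, possibly related, not serious | Not reported | SAE | Not an AE, so not an SAE |
| Expected severity, possibly related, serious outcome | Not reported | SAE | Not an AE, so not an SAE |

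Row 1 is consistent.

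Row 2 is conflict (a). Once the finding is more severe than expected, 14.6.1 allows it to be an AE. With no listed outcome under 14.6.2, and applying 14.6.5, it stays an AE. The NOTE makes it an SAE.

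Rows 3 and 4 are conflict (b). The 9.1.3 lead sentence and 14.6.1 except severity only, so relatedness does not bring the finding back into AE reporting, and 14.6.2 then bars SAE status. The NOTE requires SAE status. The conflict is therefore also internal to 9.1.3, between its first sentence and its NOTE. Row 4 matters most: a hospitalization for disease symptoms of expected severity, judged possibly drug-related, is a mandatory SAE under the NOTE and matches an example 14.6.2 gives of what cannot be one. A similar gap arises for events that exceed expectation in frequency or duration but not severity, because the NOTE counts those and the other two texts do not.

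Reach of the effect in the outputs:

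- Protocol 11.5.2.5 would give SAE frequencies and proportions.
- SAP Sections 1 and 2.1 drop all summary tables. Five subjects enrolled and only listings are produced.
- Extra non-serious events would appear in Listing 25 (non-fatal SAEs). They cannot enter Listing 24 (fatal SAEs), because death is itself a seriousness outcome.
- The documents give no rate of disease-related events or SAEs, so no misclassification rate can be computed.

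**The case against.** The strongest defence is a narrower reading. The heading is "Disease-Related Events and/or Disease-Related Outcomes Not Qualifying as SAEs", and the NOTE chooses between an SAE and a DRE. It could therefore be meant only for events that already have a serious outcome and were set aside as disease-related, such as the examples in 14.6.2. Section 9.1 points to Appendix 6 for definitions, and Section 9.1.2, immediately before, sends abnormal laboratory results and other safety assessments to AE or SAE reporting according to those definitions. For worse-than-expected findings, the 9.1.3 lead sentence itself leaves an AE route open.

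This weakens conflict (a) but does not remove it, because the body text covers all clinically significant disease-associated assessments and never limits itself to serious ones. It leaves conflict (b) untouched. Even if the NOTE is confined to serious outcomes, an event of expected severity that is possibly related must be an SAE under the NOTE and cannot be one under 14.6.1 and 14.6.2.

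The defence is right about consequences. SAEs are one of several components of a descriptive primary endpoint, with no hypothesis test (Section 11.1). The escalation and MTD rules turn on DLTs, not SAE status (Tables 2 and 3, Section 11.2.1).

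**Conclusion.** The contradiction stands and the text is wrong as written. It should be fixed, but its measurable effect is small. Applied literally, the NOTE could add unnecessary 24-hour reports and lines in Listing 25, and could have raised the SAE summary that the protocol planned. If Appendix 6 is followed instead, possibly drug-related serious events could be missed. Both outcomes depend on how sites read the text, and the documents do not show that either happened.

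A reader might infer more, and the documents do not support it:

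- *That the SAE count in the primary endpoint is in fact inflated.* This assumes literal use of the NOTE at sites, and the SAP reports no SAE count or proportion.
- *That one misfiled event shifts the SAE proportion at a dose by 33% to 100%.* That is simply 1/n for cohorts of 3 and 1. Table 2 and Section 4.2 allow 6, 12 and 18 subjects, where 1/6 = 17%, 1/12 = 8% and 1/18 = 6%. None of these figures says how often misfiling occurs.
- *That the fatal SAE listing fills with non-serious events.* By definition it cannot.

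**What to change.** Reconcile the passages with three edits.

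1. Change the NOTE so that an event meeting either trigger is recorded and reported as an AE, or as an SAE when it meets a seriousness criterion in Appendix 6, in place of DRE status. This resolves conflict (a).
2. Add a second exception, for a reasonable possibility of relationship to treatment, to the 9.1.3 lead sentence and to the disease-related items in the 14.6.1 list of events that are not AEs. This resolves conflict (b). Changing the NOTE alone would not. The wording on severity, frequency and duration can be aligned at the same time.
3. Define DRE.

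For existing data, check each Listing 25 entry against the Appendix 6 seriousness criteria. That finds over-reporting only. Events withheld as disease-related would have to be sought in the subjects' records.

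The cost is a few sentences of text and a check of five subjects' data. Sites following the NOTE would file fewer non-serious events as 24-hour reports.
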